A feasibility randomised controlled trial on the efficacy of the WHO's 'Caregiver Skills Training programme'

Statistical Analysis Plan

ISRCTN: 58638141

Description of the trial

This study will assess the feasibility of a randomised controlled trial (RCT) with a 1:1 allocation ratio to a Caregiver Skills Training (CST) intervention group and a control group. The CST intervention is composed of multiple components delivered over a period of approximately 4 months: 9 Group Sessions, 3 Virtual Home Visits, and 4 Telephone Calls over the course of the intervention period. Families will be enrolled in 4 blocks of 20 caregivers in each block, for a total of 80 families. Half will be randomized to receive the intervention and the other half in the control group. Families in the control group will be offered intervention after a waiting period that corresponds to the completion time of the CST programme.

Research objectives

The overall aim of the study is to examine the extent to which the Caregiver Skills Training (CST) programme trial can be feasibly implemented in the study setting. Specifically, we aim to fulfil the following objectives:

Primary objective:

[figure not shown]
• Feasibility and adherence: obtain estimates of participant recruitment and retention rates, data completeness/adequacy, and intervention adherence.

Secondary objectives:

 Obtain preliminary effect estimates of CST on caregiver-child interaction, child language, child emotional and behavioural problems, caregiver distress and caregiver empowerment to power a future large-scale trial.

Trial design

Figure 1 shows the trial flowchart with various stages of the trial and Table 1 details the assessment tools used in each stage. REDCap system will be used to support data capture and monitoring forms for questionnaires, direct assessments, and delivery of the intervention.

Page 3 of 10

Table 1: Assessment tools with time of collection and variables specified for summary/analysis in SAP

summary/analysis in SAP Measure	Enrolment	Baseline	Interventio	Follow-up	Variable extracted
CST Screening Form	х				 Number of sites referring to the study Number of caregivers referred by each site Number & proportion of caregivers eligible Child chronological age
CST Consent Form for Caregivers	х				Number & proportion of caregivers consented
Randomization Form	х				Number of participants randomised by trial arm
Withdrawal Form	x	Х	Х	Х	Number of participants who withdraw

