- 2. The child is suspected of or diagnosed with ASD, a global developmental delay, an intellectual disability, or any other related neurodevelopmental condition,
- 3. The child is either pre-verbal or has language abilities that are lower than what is expected for their age, i.e., no more than 3 words in length,
- 4. The primary caregiver, i.e., the individual responsible for the daily care and upbringing of the child, including parents, grandparents, or any other adult over the age of 18, can attend all relevant assessment and intervention activities.

Participants will be excluded if they meet any of the following:

- 1. Child is already enrolled in an intensive treatment program (more than 14 hours a week)
- 2. Any factor interfering with the caregiver's ability to complete the program; for example, limited knowledge of English; limited or unstable contact with the child; no access to a computer, tablet or laptop, or a secure internet connection.

Eligible caregivers will be consented to their own and their child's participation in the study. A number of demographic and clinical characterization measures outlined in Table 1 will be collected.

Baseline: Once a block of 20 families have been consented, 10 families will be randomised to receive the CST Programme right away and 10 will be randomized to a wait-list control (treatment as usual). Enrolled participants will complete the measures outlined in Table 1.

Allocation: Once eligible participants have consented, caregiver-child dyads will be randomly allocated to either the immediate CST or control group with a 1:1 ratio and stratified by preferred language (English vs. French in the Quebec sites). Simple randomisation will be performed using random numbers programmes in R-CRAN (version 3.3.0) by an assigned team member who is not involved in the study in any other capacity.

The numbers generated and the randomisation will only be accessible to this team member to ensure concealment. The randomisation procedure will begin once all the families for each block have been recruited.

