Participants in the intervention group will receive the CST intervention immediately following enrolment (9 group sessions, 3 home sessions, 4 phone calls). At that time, the waitlist control group will only have access to CST intervention materials, namely the Participant Booklets then wait to receive the full interventions 4-5 months after randomization. Trained interventionists who will offer CST to participating families (called Master Trainers) will also read and sign a consent form to be returned to the research team either electronically or by mail. A number of measures will be collected by the Master Trainers and by the research team to examine intervention adherence and fidelity of interventionists while they deliver CST to both the experimental and control groups.

Follow-up: After the first group of 10 families allocated to the intervention have completed the intervention, all 20 families will undergo follow-up assessments as outlined in Table 1.

Blinding: Due to the nature of the intervention, neither the interventionists nor the families can be blinded to allocation. Every effort will be made to ensure that outcome measures are administered by the research team who are not involved in the intervention delivery and are blinded to treatment allocation. The research team will enter data directly into the online data collection platform to ensure that data monitoring can occur without unblinding. Group assignment will not be revealed until the end of the study after database lock.

Sample size estimation

In line with guidance on feasibility studies, no power calculation has been carried out (Arian et al., 2010). A sample size of 60 to 100 has been shown to be sufficient in a feasibility trial (Moher et al., 2001). A target sample size of 80 (N=40/arm) will be enrolled and randomised based on the practical number of participants who can be recruited to undergo the CST programme at each recruitment site considering the available resources at each recruitment site.

Data monitoring

After the completion of the first programming block, a brief data check will be conducted by an independent analyst. The analyst will request pooled data extracts (no information on participant treatment allocation) to analyse and report the following:

- Summary of numbers initiating the enrolment/intake stage, consented, completing baseline, randomised, and those completing follow up
- Descriptive statistics for baseline demographic measures

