Data analysis will be done in Stata (Version 17.0 or higher). Distributional assumptions for regression models will be checked using visual methods (i.e. plots of residuals to check if residuals are normally distributed, scatterplots of standardised residuals to check homoscedasticity) and nonparametric approaches used where necessary.

Preliminary effect estimates for CST outcomes will be produced along with 95% CIs and p-values but treated as exploratory. Outcomes will be analysed using multivariable linear regression analysis. Continuous outcomes will be modelled using linear regression, with post-intervention score predicted by the following (fixed effects): treatment (CST or control), stratifier (French or English), and baseline measurements of continuous outcomes. Mean differences with 95% confidence intervals in continuous outcomes between trial arms will be reported. Other ad-hoc analyses may be requested by the trial clinical team.

Adverse event reporting

No information on adverse events will be collected.

Loss to follow-up and other missing data

The number and proportion withdrawing and lost to follow-up will be summarised overall and by trial arm. If reasons for withdrawal have been captured, these will be summarised overall and by trial arm. The number and proportion of participants missing each measure will be summarised overall, as well as in each arm and at each time point as appropriate.

Missing data will be assessed for randomness, and if missing values were missing completely at random, appropriate methods such as imputation using the overall sample mean will be considered. Since this is a feasibility study, we will not make inferential conclusions about differences between arms. Where appropriate, 95% CIs will be reported. P-values may be reported but will be treated as exploratory. There are no significance thresholds for secondary outcomes.

For individual scales, we will use published guidance on how to handle missing values. If such guidance is not available, scales may be pro-rated for an individual if 20% or fewer items are missing and pro-rating is appropriate. If there are more than 20% missing items, the scale score will not be calculated and will be missing.

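### The outcome model treats all families as independent, so its confidence intervals may be too narrow if outcomes correlate within CST groups; it also omits block, which works the other way

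*SAP*

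**What the plan says.** Under Description of the trial, the SAP describes the intervention as "9 Group Sessions, 3 Virtual Home Visits, and 4 Telephone Calls over the course of the intervention period". The same section says "Families will be enrolled in 4 blocks of 20 caregivers in each block, for a total of 80 families".

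Under Trial design, the Baseline paragraph says "Once a block of 20 families have been consented, 10 families will be randomised to receive the CST Programme right away" and assigns the other 10 to the wait-list. The Allocation paragraph describes allocation "with a 1:1 ratio and stratified by preferred language (English vs. French in the Quebec sites"), then adds "Simple randomisation will be performed using random numbers programmes in R-CRAN (version 3.3.0"). It also says that randomisation starts once each block has been recruited. Until follow-up, wait-list families have only the Participant Booklets. Follow-up is timed by block: "After the first group of 10 families allocated to the intervention have completed the intervention, all 20 families will undergo follow-up assessments".

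Under Secondary Objective: CST Effect Estimates, "Outcomes will be analysed using multivariable linear regression analysis", "with post-intervention score predicted by the following (fixed effects): treatment (CST or control), stratifier (French or English), and baseline measurements of continuous outcomes". The planned residual checks cover normality and homoscedasticity. The SAP nowhere mentions clustering, an ICC, a group or block effect, or robust standard errors.

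The resulting intervals and p-values are labelled exploratory. Under Research objectives, however, the effect estimates are meant to help power a later large trial.

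**The concern.** Two features of the design are missing from the model, and they have different consequences.

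**Group delivery.** CST families who attend sessions together may end up with more similar outcomes than families who do not. Control families share no sessions before follow-up, so any such correlation arises in one arm only (a partially nested design). Ordinary regression assumes independent residuals. If the within-group correlation is positive, it understates the standard error of the CST effect, and the planned residual checks would not show this.

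**Block.** Families enter in four successive blocks with a stated 10/10 split in each. If blocks differ in outcome level, that variation cancels out of the treatment comparison but stays in the residual, so the reported standard error is slightly too large.

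What is at stake is mainly the later trial. If it is also delivered in groups, its sample size needs an allowance for clustering, and the planned output neither supplies one nor warns that one is needed.

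**Working it through.** **Inputs from the SAP.** There are 4 × 20 = 80 families and 4 × 10 = 40 per arm, which reproduces the target under Sample size estimation. No power calculation is stated, so there is no other figure to reproduce. Ten is the number of CST families per block and hence the upper limit for a session group within a block.

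**Assumptions not in the SAP.** Session-group size m = 5 or 10; ICC 0.01 to 0.10; block variance 0.05 to 0.10; baseline–follow-up correlation 0.6 where baseline adjustment is shown.

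**1. Clustering in the CST arm only.** The design effect is DE = 1 + (m − 1) × ICC. With equal arms, true SE / reported SE = √((DE + 1)/2), and coverage = 2Φ(1.96/ratio) − 1.

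| m | ICC | DE | SE ratio | Coverage |
|---|---|---|---|---|
| 10 | 0.01 | 1.09 | 1.02 | 94.5% |
| 10 | 0.05 | 1.45 | 1.11 | 92.3% |
| 10 | 0.10 | 1.90 | 1.20 | 89.6% |
| 5 | 0.05 | 1.20 | 1.05 | 93.8% |
| 5 | 0.10 | 1.40 | 1.10 | 92.6% |

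A simulation of the SAP model (6,000 runs per setting, m = 10, ICC on the scale of the residual after baseline adjustment) gave coverage of 92.7% at ICC 0.05 and 89.2% at ICC 0.10.

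**2. The scale of the ICC matters.** Suppose instead that the group variance is 0.05 or 0.10 of the outcome variance before baseline adjustment. With correlation 0.6 the residual variance is 1 − 0.36 = 0.64.

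- Group variance 0.05: true SE = √(0.05/4 + 2 × 0.64/40) = √0.0445 = 0.211.
- Group variance 0.10: true SE = √(0.10/4 + 0.032) = √0.057 = 0.239.

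Simulation gave 0.212 and 0.238, against reported values of 0.182 and 0.185. The ratios are 1.16 and 1.29, and coverage is about 91% and 87%. On the residual scale these settings are ICC 0.05/0.69 = 0.072 and 0.10/0.74 = 0.135, which is why they look worse than the table.

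**3. Leaving out block.** With 10/10 in each block, block effects cancel from the difference between arms. The expected between-block sum of squares is 20 × 3 × block variance. It enters a residual with 80 − 4 = 76 df, so the residual variance rises by 60/76 = 0.79 of the block variance.

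- Block variance 0.05: √((0.64 + 0.79 × 0.05)/0.64) = 1.03.
- Block variance 0.10: √((0.64 + 0.79 × 0.10)/0.64) = 1.06.

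Simulated reported SEs were 0.185 and 0.190 without block, against 0.179 and 0.180 with it. If block variance is instead set against a unit residual variance, the excess is about 2% to 4%, and simulated coverage without block is 95.6% to 95.8%.

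**4. Block alone does not cure the clustering.** With block fixed effects and no group term, simulated coverage was 93.0% at ICC 0.05 and 90.3% at ICC 0.10.

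**5. The randomisation text.** Under simple 1:1 randomisation of 20 families, an exact 10/10 split has probability C(20,10)/2²⁰ = 184,756/1,048,576 = 17.6%. The Baseline and Allocation paragraphs therefore describe different procedures.

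**The case against.** The strongest reply is that little depends on these intervals. They are secondary and exploratory, there are no significance thresholds, and the SAP says it will draw no inferential conclusions about differences between arms. Ignoring clustering does not bias the point estimate. This limits the weight of the point but does not remove it, because the SAP still commits to 95% intervals and intends the estimates for planning.

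A second reply is that the inputs are assumed. The SAP does not say how many families share a session group, whether language splits groups further, or how Master Trainers are assigned. Seven of the 16 contacts (three home visits and four calls) are not group sessions. All of this stands, and it is why the result is given as a range.

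A third reply concerns the textbook remedy, a partially nested mixed model. With one CST group per block and block in the model, the group variance rests on 3 df. The estimate would fall at zero in about 50% of trials at a true ICC of 0.05 and 41% at 0.10, and the model then returns roughly the ordinary interval. Otherwise the critical value can approach 3.18 instead of 1.99, about 1.6 times larger. An estimated ICC of 0.05 from four groups of 10 would have a 95% interval from below zero to about 0.67. This also stands: such a model should not be the required analysis.

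A reader might infer that the planned intervals are simply wrong. The SAP does not support that. The ICC is unknown, the effect at ICC 0.01 is negligible, and the two omissions act in opposite directions.

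**Conclusion.** The point holds in a limited form. The model omits both CST group and block, and nothing else in the SAP makes up for it. The intervals and p-values will be too optimistic if the within-group correlation is positive. At ICC 0.05 to 0.10 on the residual scale, coverage falls to about 92% to 90% with groups of 10, or 94% to 93% with groups of 5. These figures depend on assumed ICCs and group sizes. Omitting block is the lesser matter: it costs a few per cent of precision and is conservative. That conclusion assumes the 10/10 split per block is what is done, which the Allocation paragraph leaves unclear. The change should be made because it is cheap and the estimates are meant for planning; it does not threaten the primary feasibility objective.

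**What to change.** 1. Reconcile the simple randomisation named in the Allocation paragraph with the 10/10 split per block in the Baseline paragraph.
2. Then add block (4 levels) as a fixed effect in each outcome model.
3. Record which CST group each family attended, and the group sizes.
4. Beside each ordinary interval, report a sensitivity interval with the standard error multiplied by √((DE + 1)/2), using the actual group size and stated ICCs (for example 0.01, 0.05 and 0.10). State that the ICC is on the residual scale.
5. Optionally, give a partially nested mixed model with small-sample degrees of freedom and its ICC as descriptive output, stating that about four groups make it very imprecise.
6. State that sample-size planning for the later trial must allow for group clustering. For the same one-arm structure with groups of 10, the factor (DE + 1)/2 is (1.45 + 1)/2 = 1.23 at ICC 0.05 and (1.90 + 1)/2 = 1.45 at ICC 0.10.

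The cost is SAP wording, three degrees of freedom for block, a little more analysis and somewhat wider sensitivity intervals. The only added data item is group membership.

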Missing baseline data should be limited as participants are ideally not randomised before completion of pre-randomisation measures. If there are missing items at baseline for secondary outcomes, appropriate imputation methods may be applied (i.e. mean imputation; White and Thompson (2015). The research team will make every effort to minimise missing data at follow-up. If there is a considerable amount of missing values in secondary outcomes (>15% missingness), baseline predictors of missingness will be investigated. Baseline variables found to predict missingness in secondary outcomes will be included in adjusted regression models for secondary outcomes to make the missing at random assumption more plausible.

References

- White IR, Thompson SG (2005). Adjusting for partially missing baseline measurements in randomized trials. Stat Med, 15;24(7):993-1007.

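### The overall-mean imputation option is not confined to baseline; applied to follow-up outcomes it would shrink a real CST effect by about the missing fraction

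*SAP*

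**What the plan says.** The SAP section *Loss to follow-up and other missing data* opens with loss to follow-up and with measures missing at each time point. It then says that "if missing values were missing completely at random, appropriate methods such as imputation using the overall sample mean will be considered". It names no other imputation method for follow-up outcomes.

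Later in the same section, baseline has its own rule: "If there are missing items at baseline for secondary outcomes, appropriate imputation methods may be applied". The example given there is mean imputation, with a citation to a paper on partially missing baseline measurements. For secondary outcomes with more than 15% missing, the plan looks for baseline predictors of missingness and adds them to the regression "to make the missing at random assumption more plausible".

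The analysis model is a linear regression of the post-intervention score on "treatment (CST or control), stratifier (French or English), and baseline measurements of continuous outcomes". On reporting, the plan says: "Mean differences with 95% confidence intervals in continuous outcomes between trial arms will be reported". The secondary objective is to obtain effect estimates for powering a future large trial.

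**The concern.** Filling a missing baseline covariate with the overall mean is a recognised device in a randomised trial, because the covariate is measured before treatment. Filling a missing outcome with the mean of both arms combined is a different operation. It gives an untraced CST family and an untraced control family the same follow-up score, so those families contribute no treatment difference while still counting as observed.

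The condition attached to the option does not protect it. When outcomes are missing completely at random (MCAR), the planned regression on observed outcomes is already unbiased. The option would therefore replace an unbiased estimate with an attenuated one. At stake are the mean difference and the outcome SD, which are the quantities a later trial would take from this one.

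**Working it through.** **Inputs from the SAP.** On sample size: "A target sample size of 80 (N=40/arm) will be enrolled and randomised". The model has treatment, language and baseline score as predictors. The plan forecasts no missingness rate; 15% is its own threshold for a considerable amount. Since "no power calculation has been carried out", there is no planned figure to reproduce.

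**Assumed inputs.** Outcome SD 1; true difference 0 to 0.8 SD; baseline-to-follow-up correlation r of 0.5 or 0.6; MCAR missingness of 10% to 30%, equal in the arms unless stated.

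**1. Arm difference.** Let a fraction m be missing in each arm and filled with the pooled mean M.
- CST mean: (1−m)μ₁ + mM. Control mean: (1−m)μ₀ + mM.
- Difference: (1−m)(μ₁−μ₀).
- True 0.40 becomes 0.85 × 0.40 = 0.34 at 15% missing and 0.70 × 0.40 = 0.28 at 30%.
- Unequal loss does not rescue it. With 30% missing in CST and 10% in control, 28 and 36 families are observed. For a true difference of 0.5, M = (28/64) × 0.5 = 0.219. The expected difference is 0.70 × 0.5 + 0.30 × 0.219 − 0.10 × 0.219 = 0.39 (simulated: 0.40).

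**2. Outcome SD.** The filled values sit at or near the arm's centre, so the within-arm variance is about (1−m)σ². Then √0.85 = 0.92 (8% low) and √0.70 = 0.84 (16% low).

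**3. Coverage of the 95% interval.** Simulation of the planned regression, 40 per arm, r = 0.6:

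| True difference | Missing | Mean estimate after imputation | Coverage |
|---|---|---|---|
| 0.4 | 15% | 0.34 | about 93% |
| 0.4 | 30% | 0.28 | about 88% |
| 0.8 | 15% | 0.68 | about 90% |
| 0.8 | 30% | 0.56 | about 72% |
| 0 | 10–30% | 0 | 94–95% |

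Regression on observed outcomes was unbiased, with about 95% coverage throughout.

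**4. Why coverage falls.** At a true difference of 0.4, r = 0.6 and 20% missing, the model SE (0.170) equals the empirical SD of the imputed estimate (0.170). At 30% the two are 0.163 and 0.160. The SE fits the estimator; the estimator is centred in the wrong place. A hand check at r = 0.5, true difference 0.8 and 30% missing: bias = 0.30 × 0.8 = 0.24, model SE 0.176, so the shift is 0.24/0.176 = 1.36 SE. Coverage ≈ Φ(1.99 − 1.36) = Φ(0.63) ≈ 0.74, as simulated.

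**5. Interval width** (r = 0.5, true difference 0.5). From 15% to 30% missing, the observed-outcome interval widens from 0.85 to 0.94. The imputed one narrows from 0.74 to 0.69.

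**6. Size of a later trial.** n per arm = 2(1.96 + 0.84)²σ²/Δ² (80% power, two-sided 5%). With σ = 1 and Δ = 0.5 this is 62.8, so 63.
- Attenuated difference and shrunken SD: 62.8/(1−m), which is 74 at 15% missing and 90 at 30%.
- Shrunken SD with a fixed target difference of 0.5: 62.8 × (1−m), which is 54 and 44.

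**The case against.** **It is an option, not a rule.** The wording offers an example to be considered, and only if data are judged MCAR. A reader might infer that the plan commits to mean-imputed outcomes; it does not. This lowers the severity. However, it is the only imputation method named for data other than baseline items and partly missing scales, it is called appropriate, and the choice is left until the data are seen.

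**Its reach to outcomes is inferred.** The sentence names neither outcomes nor follow-up. That is fair, but it also sets no limit, it follows text on loss to follow-up, and baseline has its own separate rule.

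**Above 15% missing the plan takes another route.** If baseline predictors of missingness are found, MCAR fails and the option lapses. If none are found, nothing rules it out. The section does not say which approach governs. At 15% missing and below, the loss of coverage is small for moderate effects, though the estimate is still low by about the missing fraction.

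**The estimates are exploratory.** The plan disclaims inferential conclusions and says "There are no significance thresholds for secondary outcomes". The primary feasibility counts are untouched. This stands as a limit on severity, but the label does not correct a biased estimate that is passed on for planning.

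**Imputation is not harmful on every measure.** At a true difference of 0.4 its root mean squared error is lower than that of the observed-outcome regression: 0.187 against 0.203 at 20% missing, and 0.200 against 0.214 at 30%. At 0.8 it is worse. A standardised effect is also attenuated less than the raw one: 0.32/0.891 = 0.36 at 20% missing, about 10% low rather than 20%. Both points stand.

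**Conclusion.** The concern holds as a fault in an optional method that the SAP does not confine to baseline. If overall-mean imputation is used for follow-up outcomes and CST has an effect, the mean difference is too small by about the missing fraction, the SD is too small, and the interval narrows as families are lost. The direction follows from algebra. The coverage figures rest on assumed effect sizes, correlation and missingness, none of which the SAP gives.

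Three stronger readings are tempting, and the material does not support them:
- That the confidence intervals are wrong in general. With no effect, the estimate is unbiased and coverage is nominal. The model SE also matches the imputed estimate's own variability, so the undercoverage comes from attenuation.
- That imputation can only do harm. The mean squared error at modest effects contradicts this.
- That a later trial would necessarily be too small. It could be too large (attenuated effect) or too small (shrunken SD with a fixed target difference).

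The plan should be changed, but the trial's primary purpose does not depend on it.

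**What to change.** In *Loss to follow-up and other missing data*, restrict mean imputation to missing baseline covariates, in line with the separate baseline rule, and remove it for follow-up outcomes. State that observed follow-up outcomes will be analysed with the planned regression (treatment, language stratifier, baseline score), adding the baseline predictors of missingness already foreseen when more than 15% are missing. This also settles which approach governs outcomes.

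Multiple imputation with trial arm in the imputation model could be added as a sensitivity analysis; it is optional.

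The cost is one or two sentences of SAP text and somewhat wider confidence intervals. No new data are needed.
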